### Complete remission (CR) rate

CR rate will be summarized for end of induction cycle 1, end of induction cycle 2, end of consolidation, after treatment discontinuation and overall. The difference in CR rates along with two-sided 95% CIs.

### Cumulative incidence of relapse (CIR)

The survival distribution of CIR distributions will be estimated using the Kaplan-Meier method, and Kaplan-Meier curves, medians and 95% CIs ([Brookmeyer and Crowley 1982](#)) of the medians will be presented for each treatment arm. The HR for CIR will be calculated, along with its 95% CI, using a stratified Cox model using the randomization stratification factors.

As a sensitivity analysis, the same analyses when patients are considered as censored at the time of the transplant if they received SCT will be performed.

## 2.8 Safety analyses

All safety analyses will be based on the safety set.

## 2.8.1 Adverse events (AEs)

Summary tables for adverse events (AEs) will include only AEs that started or worsened during the on-treatment period, the treatment-emergent AEs.

Adverse events are coded using the Medical dictionary for regulatory activities (MedDRA) terminology.

AEs will be assessed according to the Common Terminology Criteria for Adverse Events (CTCAE) version 5.0. The CTCAE represents a comprehensive grading system for reporting the acute and late effects of cancer treatments. CTCAE grading is by definition a 5-point scale generally corresponding to mild, moderate, severe, life threatening, and death. This grading system inherently places a value on the importance of an event, although there is not necessarily proportionality among grades (a grade 2 is not necessarily twice as bad as a grade 1).

AEs will be summarized by number and percentage of subjects having at least one AE in each primary system organ class (SOC) and for each preferred term (PT) using MedDRA coding. A subject with multiple occurrences of an AE will be counted only once in the respective AE category. A subject with multiple CTCAE grades for the same preferred term will be summarized under the maximum CTCAE grade recorded for the event. AE with missing CTCAE grade will be included in the 'All grades' column of the summary tables.

In AE summaries, the primary system organ class will be presented alphabetically and the preferred terms will be sorted within primary SOC in descending frequency. The sort order for the preferred term will be based on their frequency in the investigational arm

In AE summaries by phase, AEs newly recorded between the start date and the end date of the phase will be used, that is, AEs continued from the previous phases and not newly recorded will not be included in the summary. If a subject discontinued study treatment in a specific treatment phase, then all AEs observed within 30 days from the study treatment discontinuation in addition to those observed during this treatment phase will be considered.

The following AE summaries will be produced by phase and treatment group;

- overview of adverse events and deaths (number and % of subjects with any AE, any AE suspected to be related to study treatment, any SAE, any SAE suspected to be related to study treatment, any fatal SAE, any fatal SAE suspected to be related to study treatment, any AE leading to study drug discontinuation, any AE leading to study drug discontinuation suspected to be related to study treatment, any AE leading to dose reduction, any AE leading to dose interruption, AEs requiring additional therapy, AEs leading to fatal outcome)
- AEs, regardless of study treatment relationship, by SOC, PT and maximum CTC grade
- AEs, regardless of study treatment relationship, by PT and maximum CTC grade
- AEs, regardless of study treatment relationship, by SOC and maximum CTC grade
- AEs suspected to be related to study treatment, by SOC, PT and maximum CTC grade
- AEs suspected to be related to study treatment, by PT and maximum CTC grade
- SAEs, regardless of study treatment relationship, by SOC, PT and maximum CTC grade
- SAEs, regardless of study treatment relationship, by PT and maximum CTC grade

- SAEs suspected to be related to study treatment, by SOC, PT and maximum CTC grade
- Non-SAEs, regardless of study treatment relationship, by SOC, PT and maximum CTC grade
- Non-SAEs suspected to be related to study treatment, by SOC, PT and maximum CTC grade

The following AE summaries will be produced by treatment group;

- AEs leading to study treatment discontinuation, regardless of study drug relationship, by SOC, PT and maximum CTC grade
- AEs leading to study treatment discontinuation, regardless of study drug relationship, by PT and maximum CTC grade
- AEs leading to dose reduction of study treatment, regardless of study drug relationship, by SOC, PT and maximum CTC grade
- AEs leading to dose interruption of study treatment, regardless of study drug relationship, by SOC, PT and maximum CTC grade
- AEs requiring additional therapy, regardless of study drug relationship, by SOC, PT and maximum CTC grade
- AEs leading to fatal outcome, regardless of study drug relationship, by SOC and PT

In addition, a summary of non-SAEs with number of occurrences will be produced (an occurrence is defined as >1 day between start and prior end date of record of same preferred term) as per EudraCT requirements.

All AEs will be listed and those collected during the pre-treatment and post-treatment period will be flagged.

### **2.8.1.1 Adverse events of special interest / grouping of AEs**

#### **Data analysis of AESIs**

An adverse event of special interest is a grouping of adverse events that are of scientific and medical concern specific to compound midostaurin. These groupings are defined using MedDRA terms, SMQs (standardized MedDRA queries), HGLTs (high level group terms), HLT (high level terms) and PTs (preferred terms) in the Case Retrieval Sheet. Customized SMQs (Novartis MedDRA queries, NMQ) may also be used. A NMQ is a customized group of search terms which defines a medical concept for which there is no official SMQ available or the available SMQ does not completely fit the need. It may include a combination of single terms and/or an existing SMQ, narrow or broad. For each specified AESI, number and percentage of patients with at least one event of the AESI occurring during on treatment period will be summarized.

Summaries of these AESIs will be provided by treatment arm, (specifying grade, SAE, relationship, leading to treatment discontinuation, leading to dose adjustment/interruption, fatal outcome, etc.). If sufficient number of events occurred, analysis of time to first occurrence of AESI (CTCAE grade  $\geq 3$ ) will be applied. The time to first occurrence of AESI will be censored at the date of the last adequate safety assessment if no AESI event (CTCAE grade  $\geq 3$ ) is observed prior to the LPLV. The date of last adequate safety assessment will be the final

timepoint for the safety before a censoring reason is occurred. If no post-baseline safety assessments are available then the date of the start of study treatment will be used.

### **2.8.2 Deaths**

Separate summaries for on-treatment, post-treatment and all (including both on-treatment and post-treatment) deaths will be produced by treatment arm, SOC and PT.

All deaths will be listed, post treatment deaths will be flagged. A separate listing of deaths prior to starting treatment will be provided for all screened subjects.

### **2.8.3 Laboratory data**

#### **CTC grading for Laboratory parameters**

Grade categorization of lab values will be assigned programmatically as per NCI Common Terminology Criteria for Adverse Events (CTCAE) version 5.0. The calculation of laboratory CTC grades will be based on the observed laboratory values only, clinical assessments will not be taken into account. The criteria to assign CTC grades are given in Novartis internal criteria for CTC grading of laboratory parameters. The latest available version of the document based on the underlying CTCAE version 5.0 at the time of analysis will be used.

For laboratory tests where grades are not defined by CTCAE version 5.0, results will be graded by the low/normal/high (or other project-specific ranges, if more suitable) classifications based on laboratory normal ranges.

A severity grade of 0 will be assigned for all non-missing lab values not graded as 1 or higher. Grade 5 is not applicable. For laboratory tests that are graded for both low and high values, summaries will be done separately and labeled by direction, e.g., sodium will be summarized as hyponatremia and hypernatremia.

#### **Imputation Rules**

CTC grading for blood differentials is based on absolute values. However, this data may not be reported as absolute counts but rather as percentage of WBC.

If laboratory values are provided as '<X' (i.e. below limit of detection) or '>X', prior to conversion of laboratory values to SI unit, these numeric values are set to X.

The following rules will be applied to derive the WBC differential counts when only percentages are available for a xxx differential

- xxx count = (WBC count) \* (xxx %value / 100)

Further derivation of laboratory parameters might be required for CTCAE grading. For instance, corrected calcium can be derived using the reported total calcium value and albumin at the same assessment using the following formula:

- Corrected Calcium (mg/dL) = Calcium (mg/dL) – 0.8 [Albumin (g/dL)-4]

In order to apply the above formula, albumin values in g/L will be converted to g/dL by multiplying by 0.1, calcium values in mmol/L will be converted to mg/dL by dividing by 0.2495.

For calculation of laboratory CTC grades 0 and 1, the normal range for derived corrected calcium is set to the same limits (in mg/dL) as for calcium.

CTC grades for the derived absolute WBC differential counts (neutrophils, lymphocytes) and corrected calcium will be assigned as described above.

## **Data analysis**

On analyzing laboratory, data from all sources (central and local laboratories (as applicable)) will be combined. The summaries will include all assessments available for the lab parameter collected no later than 30 days after the last study treatment administration date (see [Section 2.1.1](#)).

All the outputs will be provided overall and by treatment phase (induction, consolidation and continuation).

The following summaries will be produced for hematology and biochemistry laboratory data (by laboratory parameter and treatment):

- For laboratory tests where grades are defined by CTCAE version 5.0, shift tables using CTC grades to compare baseline to the worst on-treatment value
- For laboratory tests where grades are not defined by CTCAE version 5.0, shift tables using the low/normal/high/(low and high) classification to compare baseline to the worst on-treatment value.

The following listings will be produced for the laboratory data:

- Listings of all laboratory data, with CTC grades and classification relative to the laboratory normal range. Lab data collected during the post-treatment period will be flagged.
- Listing of all CTC grade 3 or 4 laboratory toxicities

## **Liver function parameters**

Liver function parameters of interest are total bilirubin (TBL), ALT, AST and alkaline phosphatase (ALP).

The number (%) of patients with worst post-baseline values will be summarized:

- ALT or AST > 3xULN
- ALT or AST > 10xULN
- TBL > 2xULN
- TBL > 3xULN
- ALT or AST > 3xULN & TBL > 2xULN
- ALT or AST > 3xULN & TBL > 2xULN & ALP < 2xULN (potential Hy's law)

## **Hematological toxicities and recovery**

The following summary tables will be provided by cycle during induction and consolidation:

- Number and percentage of patients having at least one thrombocytopenia, and among them the duration of thrombocytopenia and the time between chemotherapy (cytarabine or daunorubicin) start and non-transfused recovery from thrombocytopenia (see definitions in

[Section 2.1.1](#)).

- Number and percentage of patients having at least one neutropenia, and among them the duration of neutropenia and the time between chemotherapy (cytarabine or daunorubicin) start and recovery from neutropenia (see definitions in [Section 2.1.1](#)).
- Number and percentage of patients requiring platelet transfusion.
- Number and percentage of patients requiring red blood cell transfusion.

All blood component transfusion data will be listed.

## 2.8.4 Other safety data

### 2.8.4.1 ECG and cardiac imaging data

#### Data handling

The average of the ECG parameters at that assessment should be used in the analyses.

#### Data analysis

The number and percentage of subjects with notable ECG values collected during the on-treatment period will be presented by treatment arm.

- QT, QTcF
  - New value of  $> 450$  and  $\leq 480$  ms
  - New value of  $> 480$  and  $\leq 500$  ms
  - New value of  $> 500$  ms
  - Increase from Baseline of  $> 30$  ms to  $\leq 60$  ms
  - Increase from Baseline of  $> 60$  ms
- HR
  - Increase from baseline  $> 25\%$  and to a value  $> 100$  bpm
  - Decrease from baseline  $> 25\%$  and to a value  $< 50$  bpm
- PR
  - Increase from baseline  $> 25\%$  and to a value  $> 200$  ms
  - New value of  $> 200$  ms
- QRS
  - Increase from baseline  $> 25\%$  and to a value  $> 120$  ms
  - New values of QRS  $> 120$  ms

A listing of all ECG assessments will be produced by treatment arm and notable values will be flagged. In the listing, the assessments collected during the post-treatment period will be flagged.

Summaries of grouped AEs ('QT prolongation') defined in eCRS will be provided by phase and treatment separately for all AEs, AEs suspected to be related to study treatment and SAEs, and by treatment for AEs leading to study treatment discontinuation.

### 2.8.4.2 Vital signs

Vital sign assessments are performed in order to characterize basic body function. The following parameters were collected: height (cm), weight (kg), body temperature (°C), pulse rate (beats per minute), systolic and diastolic blood pressure (mmHg).

#### Data handling

Vital signs collected during on-treatment period will be summarized. Values measured outside of on treatment period will be flagged in the listings.

#### Data analysis

For analysis of vital signs the clinically notable vital sign criteria are provided in [Table 2-5](#) below.

**Table 2-5 Clinically notable changes in vital signs**

Vital sign (unit)	Clinically notable criteria	
	above normal value	below normal value
Weight (kg)	increase >= 10% from Baseline	decrease >= 10% from Baseline
Systolic blood pressure (mmHg)	>=180 and increase from baseline of >=20	<=90 and decrease from baseline of >=20
Diastolic blood pressure (mmHg)	>=105 and increase from baseline of >=15	<=50 and decrease from baseline of >=15
Pulse rate (bpm)	>=100 and increase from baseline of >25%	<=50 and decrease from baseline of > 25%
Body temperature	>= 39.1	-

The number and percentage of subjects with notable vital sign values (high/low) will be presented by treatment arm.

A listing of all vital sign assessments will be produced by treatment arm and notable values will be flagged. A separate listing of only the subjects with notable vital sign values will also be produced.

## 2.9 Pharmacokinetic endpoints

### Exposure to the sum of active moieties

A further exposure variable will be derived to consider the contribution of the active metabolites to the total exposure of the compound.

The exposure to the sum of active moieties combines the concentration of the parent (PKC412) and the two active metabolites (CGP52421 and CGP62221) scaled based on their relative potencies, and parent to metabolite molecular weight ratio as shown below:

$$\text{PKC412} + \text{CGP52421} * (0.06) * \frac{\text{PKC412mwt}}{\text{CGP52421mwt}} + \text{CGP62221} * (1.4) * \frac{\text{PKC412mwt}}{\text{CGP62221mwt}}$$

Where mwt is the molecular weight of each analyte is: PKC412=570.65, CGP52421=587.23, CGP62221=556.63.

The potencies of the active metabolites are different across indications.

### PK parameters

PK parameters for midostaurin and its two major metabolites CGP52421, CGP62221 will be determined using non-compartmental method(s) using Phoenix WinNonlin (Version 6.4 or later- Certara L.P.) for the patients who had full PK sampling on Cycle 1 Day 8 of the induction therapy. PK parameters listed in [Table 2-6](#) will be estimated and reported, when feasible. AUClast, AUC0-t and Cmax are defined as primary parameters (contributing to PAS definition). All others are secondary and will be determined if feasible (including CL/F).

**Table 2-6 Non-compartmental PK parameters**

AUC0-t	The area under the curve (AUC) from time zero to a measurable concentration sampling time (t) (mass x time x volume  ). Note: as the last sampling time is at 12 h, AUC0-12h will be determined after the first dose
AUClast	The AUC from time zero to the last measurable concentration sampling time after the first dose (t last ) (mass x time x volume  )
Cmax	The maximum (peak) observed plasma, blood, serum, or other body fluid drug concentration after the first dose administration (mass x volume  )
Cmin	Minimal observed pre-dose concentration (when feasible)
C3h	Concentration at 3 hours post-dose (when feasible)
Tmax	The time to reach maximum (peak) plasma, blood, serum, or other body fluid drug concentration after single dose administration (time)

Descriptive statistics (n, arithmetic mean, CV% mean, standard deviation (SD), median, geometric mean, CV% geo-mean, minimum and maximum) will be presented by treatment for PAS-full for all PK parameters defined in [Table 2-6](#) except Tmax, where only n, median, minimum and maximum will be presented.

All individual PK parameters will be listed using the PAS-all.

### Concentrations for full PK profile

Descriptive statistics (n, m (number of non-zero concentrations), arithmetic mean, CV% mean, SD, median, geometric mean, CV% geo-mean, minimum and maximum) for concentrations of midostaurin, its active metabolites (CGP52421, CGP62221), and the exposure to the sum of active moieties, will be presented at each scheduled time point on C1D8 for the PAS-full. PK parameters will also be summarized by analyte. Individual concentration-time profiles for midostaurin, its active metabolites, and the exposure to the sum of active moieties, concentrations on C1D8 with median will be displayed graphically for PAS-all on the semi-log view. In addition, the mean (+/- SD) and geometric mean concentration-time profiles for midostaurin, its active metabolites, and the exposure to the sum of active moieties, on C1D8 will be displayed graphically for PAS-full on the linear and semi-log view.

All individual plasma midostaurin, its active metabolites, and the exposure to the sum of active moieties concentration data will be listed for the PAS-all.

### **Concentrations after multiple dosing**

Descriptive statistics (n, m (number of non-zero concentrations), mean, CV% mean, SD, median, geometric mean, CV% geo-mean, minimum and maximum) for midostaurin, its active metabolites, and the exposure to the sum of active moieties, concentration will be presented at each scheduled time point (post-dose or pre-dose) by treatment part for the PAS-all.

The mean (+/- SD) and geometric mean trough concentration-time profiles for midostaurin, its active metabolites, and the exposure to the sum of active moieties, over time will be displayed graphically by treatment part for PAS-all on the linear view.

All individual plasma midostaurin, its active metabolites, and the exposure to the sum of active moieties, concentration data will be listed for the PAS-all.

### **Handling of PK data below LLOQ or missing**

All concentration values below the lower limit of quantitation (LLOQ) (<10.0 ng/mL) are set to zero by the Bioanalyst, and will be displayed in the listings as zero and flagged. LLOQ values will be treated as zero in any calculations of summary statistics, and treated as missing for the calculation of the geometric means and their CV%. The number of non-zero concentrations will also be reported in the summary statistics.

Missing values for any PK data will not be imputed and will be treated as missing.

## **2.10 PD and PK/PD analyses**

### **Special population**

The association of trough concentrations of midostaurin, its active metabolites, and the exposure to the sum of active moieties on C1D21 of Induction therapy, and FLT3 status will be investigated using a Wilcoxon test.

### **Analysis of relationship between PKC412 exposure and efficacy/safety endpoints.**

All exposure-response analyses will be conducted on parent midostaurin, its active metabolites, and the exposure to the sum of active moieties. PAS-all will be used however Part 1 patients will be excluded for efficacy related analyses.

EFS will be analysed using a Cox regression model with log-transformed concentration on C1D21 as covariate. Hazard ratios will be provided for a 2-fold decrease in exposure, along with 95% CI.

OS will be analysed using a Cox regression model with log-transformed concentration on C1D21 as covariate.

The occurrence of CR in cycle 1 or 2 of induction therapy will be modelled against log-transformed Cmin (continuous and categorical) of midostaurin and metabolites on C1D21 through a logistic regression model. Furthermore, the CR rate for the median observed Cmin C1D21 along with 95% CI, will be produced. Further the point estimate of the odds ratio of response for a 2-fold decrease in exposure, and corresponding 95% CI will also be produced.

AESIs suspected to be study drug related will be analysed with the last observed trough concentration collected prior to AE onset (log-transformed), with a logistic regression model. Probability of an AESI will be estimated along with 95% CI for the median concentration used in the analysis. Further point estimates of the difference in probability of response for a 2-fold increase in exposure, and corresponding 95% CI will also be produced. Time to onset of AESI will also be investigated with a Cox regression model, and HRs related to a 2-fold increase in exposure with corresponding 95% CIs will be produced.

AEs leading to discontinuation will also be analysed with log-transformed concentration (last observed trough concentration prior to AE onset) as for AESIs. PK/PD analyses related to AESI may not be performed if the number of AESI events are limited such as less than 10 events.

A linear mixed effects model will be used to fit the change from baseline in QTcF as a response variable, with time-matched concentration (of midostaurin and both metabolites), baseline parameter and relevant covariates (identified through backwards selection) fitted as fixed effects.

Time-matched QTcF assessments and concentrations are defined as both non-missing and non-zero concentrations. Assessments are taken within a 30 minute window of each other. When there are multiple matching concentrations within a 30 minute window of the ECG assessment (or vice versa), the closest time match should be selected. When there is more than one closest match (before and after), then the PK sample should be after the ECG assessment.

Only observations where the ECG machine was synchronized will be considered. Subject ID will be fitted as a random effect. The change from baseline will be estimated (with 95% CI) for the median observed Peak Cmin at the therapeutic dose (50mg bid), the median of the observed values for each continuous covariate, and the level of the factor with higher observed frequency.

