6.5.3 Treatment blinding

Patients, investigators, study team members, and anyone involved in the study conduct will remain blinded to the identity of the study drug from the time of randomization until database lock for the primary analysis.

Randomization data will be kept strictly confidential until the time of unblinding and will not be accessible to anyone involved in the conduct of the study except for an independent statistician and an independent programmer who will perform the interim analysis and the bioanalyst to avoid the unnecessary analysis of placebo samples. The identity of the study drug

will be concealed by the use of study drug (midostaurin or placebo) that is identical in packaging, labeling, schedule of administration, appearance, and odor. Confidentiality of randomization data is required to limit the occurrence of potential bias arising from the influence that the knowledge of treatment may have on the recruitment and allocation of patients.

Unblinding of study drug assignment will only occur in the case of patient emergencies ([Section 8.3](#)) and at the time of the primary analysis (see [Section 10.7](#)). Although not anticipated, for any health authority that requests such information, every effort will be made to have an independent team respond to the request while keeping the study team blinded. In rare cases when unblinding occurs because of emergency patient management, the actual treatment arm will not be communicated to any Novartis employee involved trial conduct in order to maintain their blinded status.

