#### **2.1.1 General definitions**

##### **Investigational drug and study treatment**

**Investigational drug** will refer to the midostaurin. **Control drug** will refer to the placebo. The **study drug** will refer to investigational and control drugs. Whereas, **study treatment** will refer to treatment with daunorubicin, cytarabine, or midostaurin/placebo.

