### **Other**

#### **Pharmacokinetic analysis set for all (PAS-all)**

The Pharmacokinetic analysis set for all (PAS-all) includes all patients who took at least one dose of midostaurin and provide at least one evaluable PK concentration.

For a concentration to be evaluable, patients are required to:

- Take the planned dose of midostaurin prior to sampling
- For pre-dose samples: do not vomit within 4 hours after the dosing of midostaurin prior to sampling, have the sample collected before the next dose administration
- For post-dose samples: do not vomit within 4 hours after the dosing of midostaurin

The PAS-all will be the primary population used for all pharmacokinetic analyses using trough concentration data.

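### The planned QTcF-concentration estimate has no post-chemotherapy, drug-free reference, so a background shift common to all retained pairs passes into it in full

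*SAP*

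**What the plan says.** SAP 2.10 fits a linear mixed model to the change from baseline in QTcF. The covariates are time-matched concentration of midostaurin and both metabolites, and "baseline parameter and relevant covariates (identified through backwards selection) fitted as fixed effects", with a random subject effect. No treatment-arm, visit or time term is named.

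- **Population.** For all exposure-response work, "PAS-all will be used however Part 1 patients will be excluded for efficacy related analyses". PAS-all "includes all patients who took at least one dose of midostaurin and provide at least one evaluable PK concentration" (SAP 2.2). Part 1 patients are removed only from the efficacy models, so they stay in this one.
- **Pairs.** "Time-matched QTcF assessments and concentrations are defined as both non-missing and non-zero concentrations". Values below the 10 ng/mL quantification limit are set to zero (SAP 2.9). Placebo samples are not assayed: Protocol 6.5.3 gives treatment codes to "the bioanalyst to avoid the unnecessary analysis of placebo samples".
- **Baseline.** For safety data it is the last value on or before the start of study treatment (SAP 2.1.1). Study treatment "will refer to treatment with daunorubicin, cytarabine, or midostaurin/placebo", so it starts with chemotherapy on Day 1. The scheduled baseline ECG is on Day -3 to -1 (Protocol Table 7-4). Study drug starts on Day 8.
- **Reported result.** "The change from baseline will be estimated (with 95% CI) for the median observed Peak Cmin at the therapeutic dose (50mg bid".

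**The concern.** The reported figure is a change from a state before chemotherapy to a state after chemotherapy and on midostaurin. Nothing in the fitted data shows QTcF after chemotherapy without midostaurin. Whatever chemotherapy, electrolyte disturbance or supportive drugs do to QTcF between screening and the retained pairs is therefore part of the figure.

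The result is stated with a 95% CI at the therapeutic dose, so it is likely to be read as a midostaurin effect. The trial is randomised and placebo-controlled, and both arms follow the same ECG schedule. The reference data are collected and then left out of the model.

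**Working it through.** The documents state no slope, predicted change or precision for this model, so there is no planned figure to reproduce.

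**Which pairs survive.** These are the time points that appear in both Protocol Table 7-4 (ECG) and Table 7-5 (PK).

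| Phase | Scheduled pairs |
|---|---|
| Induction 1: Days 8, 11, 21, pre-dose and 3 h | 6 |
| Consolidation 1 and 3: Days 8, 21, pre-dose and 3 h | 8 |
| Continuation: cycle 5 Day 1, cycle 9 Day 1, cycle 12 Day 28 | 3 |
| Total from visible rows | 17 |

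A pre-continuation sample probably makes 18. The 22 visible PK rows give 22 x 3 = 66 mL against a stated 69 mL, sample number 120 is skipped, and Table 7-1 marks PK sampling before the first continuation cycle. The conclusion is the same with 17 or 18.

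Placebo patients lose every pair. Midostaurin patients lose the induction 1 Day 8 pre-dose pair for all analytes, because no study drug has yet been given.

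The consolidation Day 8 pre-dose samples are no substitute. The shortest gap from the last dose (Day 21 evening, next cycle starting 28 days after the previous one) is about 348 h. With the half-lives in Protocol 1.2.1.2, the fraction left is 2^-(t/half-life):

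- midostaurin: 2^-(348/20.5), about 0.001%, so effectively zero and dropped;
- CGP52421: 2^-(348/471), about 60%. A level of about 10/0.60 = 17 ng/mL before the gap is enough for the pair to be kept, but that pair is not drug-free.

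**What a shift does.** Write the model as

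change = a + b x C + g x baseline + u + e.

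The reported value is a + b x C* + g x baseline*. Add B to every retained on-treatment QTcF: a becomes a + B, while b and g do not move. The reported value rises by B. This is exact and holds whether one or three analytes are in the model.

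**Numerical check.** Assumed inputs, not from the documents: 30 patients per arm; the 17 pairs, three of them Day 8 pre-dose with parent concentration 0, leaving 14 retained, 11 of these in chemotherapy phases; slope 2 ms per 1000 ng/mL; typical concentrations 1100 to 3800 ng/mL; SDs 6 ms between and 8 ms within patients; an assumed dropout pattern; 60 data sets per setting. The true drug effect at the median concentration is 3.05 ms.

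| Estimate (ms) | B = 0 | B = 5 | B = 10 | B = 15 |
|---|---|---|---|---|
| Planned, shift in all pairs | 3.03 | 8.03 | 13.03 | 18.03 |
| Planned, shift in induction and consolidation only | 3.03 | 7.63 | 12.23 | 16.83 |
| Midostaurin zero-concentration pairs restored, same reported quantity, shift in all pairs | 3.11 | 8.11 | 13.11 | 18.11 |
| Placebo ECGs and zero pairs at C = 0, visit term, slope x C* reported, either shift pattern | 3.13 | 3.13 | 3.13 | 3.13 |

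In the first row the slope stays at 2.06. In the second the pass-through is (7.63 - 3.03)/5 = 0.92 and the slope goes from 2.06 to 2.20, 2.34 and 2.47. The third row shows that lifting the non-zero rule alone cures nothing. The last row was run without a treatment term.

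**The case against.** **The SAP promises only a change from baseline.** That is true, and the model delivers it. The section is about exposure and response, and the slope is not affected by a constant shift. The point concerns what the reported figure can be taken to mean.

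**No shift is shown.** The documents contain no background QTcF data, and they limit the routes to a shift. Induction chemotherapy ends on Day 7. Protocol 6.4.2 requires interruption of study drug if a drug with known torsades risk is unavoidable. Table 6-2 calls for potassium and magnesium checks when QTcF is prolonged. Two routes stay open. Drugs with possible or conditional risk may be given while treatment continues. Hypokalemia was among the commonest non-hematologic grade 3/4 events in the placebo group of Study A2301 (Protocol 1.2.1.2), and Protocol 5.3 lists it, uncorrected, as a torsades risk factor.

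**Backward-selected covariates might absorb part of the shift.** They might, but the candidates are not listed, and they cannot supply a reference that the data lack.

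**Randomised QT evidence exists elsewhere.** SAP 2.8.4.1 gives QTcF categories by arm and grouped QT-prolongation adverse events by phase and treatment. These are useful, but they compare counts and do not correct this estimate.

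**A stronger reading of the evaluability rule.** A reader might infer that the PAS-all condition "Take the planned dose of midostaurin prior to sampling" also deletes the Day 8 pre-dose record. The condition decides who enters the set. SAP 2.9 summarises concentrations at every scheduled Day 8 time point, which includes pre-dose. Only the non-zero rule clearly removes the pair.

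**Conclusion.** The point holds as a low-end minor one. The planned estimate carries any QTcF shift common to all retained pairs at exactly 1:1, whatever the other inputs. A shift confined to the chemotherapy phases enters at about 0.92 under the assumed inputs above and also moves the slope. The size of any shift is unknown; 0 to 15 ms is an assumed range.

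Three stronger conclusions are tempting and are not supported:

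- **That drug and background cannot be separated at all.** Slope times concentration from the planned model is free of a constant shift.
- **That every background shift enters in full.** This is so only when the shift is common to all retained pairs.
- **That midostaurin's QTcF effect will be overstated.** The documents establish neither that a shift exists nor its direction.

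The analysis is exploratory and has no bearing on the EFS success criterion.

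**What to change.** For this model only:

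1. Enter Part 2 placebo patients' scheduled ECGs, and the midostaurin patients' induction cycle 1 Day 8 pre-dose ECGs, at concentration 0. State that these records are exempt from the non-zero rule and from the PAS-all restriction.
2. Add treatment and nominal day/time as fixed effects and keep the baseline covariate.
3. Report the placebo-adjusted QTcF change at the stated concentration with its 95% CI.
4. Leave Part 1 patients out of that estimate, since they have no concurrent placebo group, or show them separately.

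Minimum alternative: also report slope times median concentration with 95% CI from the planned model. State that this removes only a constant shift and extrapolates linearly to zero concentration, where no pairs are kept. With a shift of 15 ms confined to chemotherapy phases, the check above still moved the slope by a factor of 2.47/2.06 = 1.20.

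The cost is SAP wording and modest reprogramming. The ECGs are already scheduled in both arms and no placebo assay is needed. The placebo-adjusted interval will probably be wider than the planned one; by how much depends on variances that the documents do not give. If the database is already locked, label the addition as post hoc.
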